1. STATEMENT OF COMPLIANCE

The study will be conducted in accordance with the Declaration of Helsinki, the International Conference on Harmonization guidelines for Good Clinical Practice (ICH E6), ISO 14155, the Code of Federal Regulations on the Protection of Human Subjects (45 CFR Part 46), and FDA regulations: 21 CFR part 50, part 54 and part 56.

All personnel involved in the conduct of this study have completed human subjects' protection training.

3. LIST OF ABBREVIATIONS

AC	Active Control
CFDA	Chinese Food and Drug Administration
CE	Capsule Endoscopy
CFR	Code of Federal Regulations
ED	Emergency Department
EGD	Esophagogastroduodenoscopy
FDA	Food and Drug Administration
GBS	Glasgow Blatchford Score
GI	Gastrointestinal
ICH	International Conference on Harmonization
IRB	Institutional Review Board
MCC	Magnetically Controlled Capsule
PCP	Primary Care Physician
RC	Research Coordinator
ST	Standard (Risk Assessment)
UC	Urgent Care
UGIB	Upper GI Bleed
US	United States

4. PROTOCOL SUMMARY

Title:	Magnetically Controlled Capsule For Assessment Of Gastric Mucosa In Symptomatic Patients: “MAGNET”
Précis:	This is a single-center prospective study examining the diagnostic utility of a single-use ingestible magnetically controlled capsule (MCC) endoscope (NaviCam™, AnX Robotica) which is remotely controlled by external hardware and software to visualize the mucosa of the stomach on patients with upper abdominal symptoms. Participants will be enrolled and tested at a central site referred from Emergency Departments (EDs), urgent cares (UCs) and primary care practices (PCPs) in the Washington, DC area and additional site(s) to be named. Total enrollment is estimated to be 72 patients with a goal of following all patients with a traditional endoscopy to confirm findings. Aim 1 is to establish feasibility of this novel outpatient testing. Aim 2 is to demonstrate high-quality visualization of gastric anatomic landmarks. Aim 3 is a pilot study to compare visualization of gastric anatomic landmarks and lesions of MCC follow-up traditional EGD. We currently anticipate enrolling 2-3 patients per week over 30 weeks.
Objectives:	
Aim 1: We aim to demonstrate feasibility of MCC in an outpatient primary and urgent care setting. Measured outcomes include duration of MCC test, linkage with EGD follow-up, image storage, image transfer, technician learning curve and documentation.
 
Aim 2: We aim to show that MCC can identify and photograph regions of stomach consistent with established visualized scoring systems for anatomic landmarks.
 
Aim 3: Pilot assessment of MCC compared to subsequent EGD to detect anatomic regions and gastric mucosal lesions.

Population:	An unselected pool of adult patients with an appropriate indication for upper endoscopy such as epigastric pain/burning, nausea and or vomiting, bloating, heartburn, iron deficiency anemia, unintended weight loss, abnormal imaging suggesting organic disease. In general, participants will be age ≥ 18 , mixed gender, mixed race, hemodynamically stable with possible co-morbidities.
Site Number	1
Study Duration:	Time needed to reach sufficient study subjects plus additional time for analysis
Subject Duration:	30 days
Estimated Time to Complete:	12 months

5. SCHEMATIC OF STUDY DESIGN:

6. INTRODUCTION: BACKGROUND INFORMATION AND SCIENTIFIC RATIONALE

6.1. Background Information

Esophagogastroduodenoscopy (EGD) is one of the most common medical procedures and indications include epigastric pain, bloating, burning, heart-burn, excessive belching, nausea and/or, vomiting, anemia, weight loss. Access to EGD is limited by the cost, the need for an endoscopy specialist and the need for anesthesia. Lack of access to an EGD is a health disparity associated with increased gastric cancer mortality-to-incidence ratio (Tsai 2017). A novel approach to visualization of the upper GI tract is needed to increase access to care and improve diagnostic capabilities. Magnetically controlled capsule (MCC) is the first wireless ingestible capsule endoscope that is able to be directed by operator to visualize all anatomic areas of the stomach (NaviCam™, AnX Robotica). This study will be the first US study to examine the feasibility of using MCC in patients with relevant symptoms to the stomach. The goal is to ascertain if the diagnostic capabilities of the MCC compared to EGD are comparable for symptomatic patients who have clinical indications for an EGD.

MCC offers potential advantages over traditional EGD including the ability to be performed 24 hours a day without sedation and to be performed by a clinician. In addition, the MCC is less invasive, does not cause discomfort, and enables the patient to pursue normal daily activities after the procedure. Non-specialist physicians can administer the MCC and interpretation can be done in real-time or asynchronously by GI specialists. The MCC may impact decisions regarding the need for hospitalization, the need for additional diagnostic testing such as biopsy, the need for additional therapeutic interventions such as endoscopic hemostasis and polypectomy, and the need for further risk stratification of disease. The eventual work-flow may be similar to that of many current diagnostic tests such as radiologic examinations. This ability to transmit images could become especially important in rural communities or in communities that have limited access to a gastroenterologist or surgeon. Incorporation of the MCC into current practice could follow a trajectory similar to that of point-of-care ultrasonography, an imaging modality in which non-radiologist physicians have become increasingly skilled and for which indications continue to expand (Bennet 2018). The American Society of Gastrointestinal Endoscopy states that credentials for capsule endoscopy should be determined independently from other endoscopic procedures such as colonoscopy, sigmoidoscopy, or any other endoscopic procedure (ASGE 2005). The American Society for Gastrointestinal Endoscopy also emphasizes that sound medical training, appropriate patient selection, correct interpretation, and continued medical management for all patients. Capsule endoscopy requires only image interpretation and does not require procedural skill training associated with other

endoscopic procedures; therefore, ED physicians, urgent care physicians and primary care doctors and mid-level practitioners can meet these criteria with basic training.

Contraindications to the MCC are similar to contraindications for established capsule endoscopy (CE) which has been performed safely in a variety of clinical settings [3]. The only absolute contraindication is intestinal obstruction [4]. There is a low risk of non-natural excretion of capsules estimated at less than 1 in 100 [5]. In general, the CE procedure poses significantly less risk than traditional EGD, and multiple studies have shown that CE is well tolerated in patients with acute symptoms (Gralnek 2008, Sung 2016, Meltzer 2013).

The cost of the capsule is an important factor that may affect future use in the ED and clinics. The use of MCC in the ED, urgent care and primary care can potentially lead to more patients being safely managed in an outpatient setting. MCC may be especially cost-effective if it reduces hospital admissions, need for anesthesia, missed work days or overall EGDs. Future technological developments in the MCC may allow for operator to collect biopsy samples and perform therapeutic functions.

6.2. Rationale

In the United States, upper endoscopy is frequently performed for a variety of symptoms including heartburn, bloating, nausea, burping, and epigastric pain/burning. The prevalence of these symptoms may provide as much as 25% of a gastroenterologist's office practice. In general, the diagnostic yield of an EGD is low. Without alarm symptoms, as many as 70% of procedures are negative for significant findings. One major indication is testing for *H. pylori* for which EGD may be unnecessary, because *H. pylori* detection can be accomplished by fecal antigen testing or breath testing as accurately as biopsy and less expensively.

We believe there is an opportunity to improve the risk stratification of patients that undergo endoscopy through the use of MCC. Our primary hypothesis is that MCC allows for visualization of the stomach of symptomatic patients referred from the emergency, urgent care and primary care settings with clinical symptoms appropriate for endoscopy. A prospective study is proposed to evaluate the feasibility, safety and accuracy of this novel diagnostic modality.

6.3. Potential Risks and Benefits

6.3.1. Potential Risks

Patients for whom study enrollment may interfere with standard clinical care will not be enrolled. Alternatives to study participation are for patient to receive standard of care treatment for symptoms which includes only an EGD or barium studies. We have considered a variety of potential risks to participants including cognitive, affective,

physical, legal/confidentiality and economic risks. The NaviCam MCC is manufactured by AnX Robotica and has been granted marketing authorization by the FDA through the de-novo process to confirm its safety and effectiveness profile.

Since its introduction to the Chinese market after being approved by the Chinese Food and Drug Agency (CFD) in 2012, the NaviCam MCC was subject to a series of clinical studies. Published studies involving more than 500 people in China have been published comparing MCC to gastroscope. In a pilot study in 34 healthy volunteers (Liao et al. 2012), 75 to 100% of gastric mucosa was visualized in 27 (79.4%) people and 50% to 75% in 7 (20.6%) people. Visualization of the gastric cardia, fundus, body, angulus, antrum and pylorus were subjectively assessed as complete in 82.4%, 85.3%, 100.0%, 100.0%, 100.0% and 100.0% respectively. In a non-blinded comparative study in 68 patients (Zou et al. 2015) showed a diagnostic accuracy similar to standard gastroscopy: the positive percent agreement was 96.0%, and the negative percent agreement was 77.8%. The overall agreement was 91.2% with a κ value of 0.765 ($p<0.001$). A total of 68 pathological findings were detected, of which 53 were identified by both methods. In a multi-center comparative study in 350 patients (Liao et al. 2016), the NaviCam detected gastric focal lesions in the whole stomach with 90.4% sensitivity, 94.7% specificity, a PPV of 87.9%, a NPV of 95.9% and 93.4% accuracy. The NaviCam was preferred by almost all patients (95.7%), compared with gastroscopy. (Liao, 2016).

The physical risks associated with the NaviCam MCC are generally related to potential non-natural excretion. There is a small risk that the capsule could become stuck in the stomach or small intestine. Based on published and unpublished data of other types of capsule endoscopes, retained capsules have persisted in the GI tract for periods for many years without adverse event. In fact, a large retrospective review by Cheifetz, et al. found that a retained capsule is often asymptomatic or leads to a diagnosis. (Chifetz 2006). Furthermore, the device is made of biocompatible materials and its internal parts are non-toxic. The incidence of capsule retention has been reported to be less than 1% but this figure may be higher in Crohn's disease or other conditions. The rate of surgical/endoscopic removal was noted to be 0.75% (Barkin, 2002).

Patients who are at increased risk of capsule retention are not appropriate study subjects including people with swallowing disorders or with known or suspected gastrointestinal obstructions, strictures or fistulas. In general, if a patient does not pass the MCC naturally through the upper GI tract due to gastroparesis, an EGD will be sufficient to retrieve the capsule. Given that all study patients will receive an EGD as part of their standard work-up for the disease, this does not pose a significant increased risk. Any patient with dysphagia will be excluded because a retained capsule in the esophagus is at risk of aspiration.

Patients will be advised not to have an MRI for 30 days. For patients who are unsure whether they excreted the MCC, *an abdominal X-Ray or "Navicam capsule locator" may be required as an outpatient to confirm passage.*

In order to maximize safety for all study subjects, only consented and enrolled subjects will be administered the MCC under the supervision of a physician and a sub-investigator/trained research associate responsible to the PI. In addition, the MCC will be stored in a secure, limited access area. Product accountability log must include the ¹² protocol number, investigative site name, product name, medical units (i.e., capsules), serial number and subject ID number.

We believe the study poses a low privacy risk to subjects as all data will be encrypted and no PHI will be stored with data. Data will be stored in a REDCap database that allows for the common collection of data from multiple sites.

Finally, the study has a low economic risk since the device and the interpretation of the device are not being billed to the subject or his/her insurance company. The follow-up EGD is considered standard of care and will be billed to the patient's insurer. AnX Robotica, the manufacturer of the NaviCam has agreed to cover the cost of medical care and treatment for research injuries sustained by subjects enrolled in the study in accordance with the terms of the Clinical Trial Agreement and there is no economic risk expected as a result of unanticipated complications of the device as these will be covered by AnX Robotica, per the final negotiated terms in the Clinical Trial Agreement (currently under negotiation).

Major adverse events that occur will be reported directly to the principal investigator and overall study coordinator within 24 hours. Minor adverse events include inability to tolerate the MCC capsule, discomfort swallowing capsule, issues regarding video capture, issues regarding video transmission, erroneous video interpretation that has no significant impact on clinical care, protocol deviations, reactions to medication (promotility agent), delays in endoscopy interpretation, delays in EGD and others. All minor adverse events will be shared with the entire research team at regularly scheduled monthly calls or sooner at the PI's discretion.

Any major adverse events that occur will be reported directly to the principal investigator who will be available to study subjects 24 hours a day. Severe adverse events will be reported to the entire research team, the sponsor, the DSMB and to IRB within 24 hours. Updates will be provided after a full investigation is completed. SAE's will also be reported to the FDA. Potential major adverse events include delayed definitive care, and capsule retention in the small bowel, and any serious outcome that may be related to study protocol. A DSMB will be formed that includes experts in primary care, emergency medicine, and gastroenterology and research methodology. DSMB of approximately 3-5 multi-disciplinary persons will meet every 6 months during which a report will be produced by PI and as needed for SAE's.

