9.3. Patient Safety

The study will be conducted in compliance with the Declaration of Helsinki, ICH-GCP guidelines, ISO 14155, and US regulations. Study design will be approved by the local IRB at each participating institution prior to commencement.

9.4. Study procedure:

1. Screen potential adult patients with an appropriate indication for upper endoscopy such as epigastric pain/burning, nausea and or vomiting, bloating, heartburn, iron deficiency anemia, unintended weight loss, abnormal imaging suggesting organic disease from a larger pool of patients seen in an ED, Urgent Care, Primary Care and GI Clinic patients. In some settings, a research assistant will be on site to perform the screen. In other settings, the clinical staff will perform the screen or potential patients will be contacted by phone by RC. (Form used: *Magnet 1*)
2. Patients screened who are eligible will be approached about potential interest. (See *full list of inclusion/ exclusion criteria*). In some circumstances, patients will be given contact information for the research coordinator (RC), who will contact them as soon as possible to schedule MCC. In other circumstances, the research assistant will contact RC and attempt to schedule MCC before patient leaves the clinical setting.
3. RC will contact patients to complete screening, confirm eligibility, obtain verbal consent, and schedule both MCC and EGD (if EGD is not already scheduled). Formal written consent will be obtained by patient at the MCC location ([name]).
4. Participants arrive at the MCC location for final screen, sign written consent and undergo MCC. All consented patients will be given a study ID and recorded in enrollment log. (Form used: *Magnet 3*) The patient's demographics and images will be stored in a HIPAA compliant fashion.
 - BRIEF DESCRIPTION OF MCC PROCEDURE. The patient will be NPO midnight. They will come to the facility and will ingest the capsule per manufacturer's protocol. (Manufacturer's protocol says that the person will take 10ml of simethicone in 100ml of water 40min before capsule is ingested. The capsule will then be controlled externally by magnetic field by the examining health care provider in such a way that the major regions of the stomach are photo-documented with still images and video. This may involve changing the position of the patient and the

possible ingestion of additional water. The sequence of the examination

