10. STUDY ENROLLMENT AND WITHDRAWAL

10.1. Subject Inclusion Criteria

1. Individuals aged \geq 18 years with upper GI symptoms (epigastric pain, bloating, burning, heart-burn, excessive belching, nausea and/or, vomiting, anemia, and weight loss) appropriate for an upper endoscopy evaluation.
2. Able to speak English
3. Able to understand and sign consent form
4. Able to undergo standard outpatient endoscopy
5. Indications for EGD Low blood (unexplained anemia)
 - Blood in vomit (hematemesis)
 - Upper abdominal or chest pain
 - Indigestion (dyspepsia)
 - GERD
 - Suspected ulcer
 - Unexplained weight loss
 - Gastric biopsy
 - Other

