10.2. Subject Exclusion Criteria

Individuals with one or more of the following will not be eligible for participation in the study:

1. Hemodynamic shock
2. Active hematemesis
3. Dysphagia, swallowing disorder
4. Suspected bowel obstruction or perforation
5. Gastroparesis
6. Crohn's disease
7. Prior GI tract surgery that changes the gastrointestinal anatomy (e.g., Billroth I or II, esophagectomy, gastrectomy, bariatric procedure and small intestinal resection)
8. Presumed pregnant, trying to conceive or currently breastfeeding
9. Altered mental status (e.g., hepatic encephalopathy) that limits the ability to swallow a capsule
10. Expected to have Magnetic Resonance Imaging examination within 30 days.
11. No reliable contact information – no phone, no permanent address.
12. Pacemaker or ICD

13. BMI \geq 38

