10.3. Strategies for Recruitment and Retention

Email notifications will be sent to GW providers on the study to help recruit eligible patients at GW EDs, urgent care facilities and PCP offices. Existing RA's stationed in those units will help spread the word about potential eligibility (i.e. stable for outpatient work-up, symptoms related to UGI tract.) Pre-screening will take place onsite. Full consent and interview for inclusion and exclusion criteria will occur by lead RC and PI at site of NaviCam.

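### Section 6.3.1 rules out people with known or suspected strictures or fistulas, but the exclusion list in Section 10.2 names neither condition

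*Protocol*

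**What the plan says.** Section 6.3.1 of the protocol discusses the risk that the capsule does not leave the body naturally. It says patients at increased risk of retention are not suitable subjects. As examples it gives people with swallowing disorders and people "with known or suspected gastrointestinal obstructions, strictures or fistulas".

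Section 10.2 sets the exclusion rule: "Individuals with one or more of the following will not be eligible for participation in the study". Thirteen items follow. Those nearest to this point are:

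- item 3: dysphagia or swallowing disorder
- item 4: suspected bowel obstruction or perforation
- item 5: gastroparesis
- item 6: Crohn's disease
- item 7: surgery that alters the GI anatomy

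Screening runs on the listed criteria. Step 2 of Section 9.4 refers to the "full list of inclusion/ exclusion criteria", and Section 17.4 names Section 10 as the place where the full criteria stand. Section 10.3 says of the last check before the capsule: "Full consent and interview for inclusion and exclusion criteria will occur by lead RC and PI at site of NaviCam".

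On the consequence, Section 6.3.1 states: "Potential major adverse events include delayed definitive care, and capsule retention in the small bowel".

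**The concern.** The protocol sets a safety limit in its risk section and does not carry it into the list that screeners apply. A screener who works through Section 10 item by item could accept a person whom Section 6.3.1 rules out.

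What is at stake is retention in the small bowel. The reassurance in 6.3.1 is that an EGD can retrieve a capsule that gastroparesis has kept from passing the upper GI tract. It describes no such remedy for a capsule held further down. Nor is the EGD certain to come after the capsule: the summary in Section 9.4 allows the capsule procedure up to 14 days before or after the EGD, and Section 13.2 expects some drop-out before EGD.

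**Working it through.** No arithmetic beyond counting applies, so the check sets the two sections side by side and then looks for the missing conditions elsewhere.

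**Step 1. The four conditions in the 6.3.1 sentence against Section 10.2**

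| Condition in 6.3.1 | Item in 10.2 |
|---|---|
| Swallowing disorder | Item 3 |
| Obstruction (known or suspected) | Item 4 (suspected, bowel) |
| Stricture (known or suspected) | None |
| Fistula (known or suspected) | None |

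Covered: 2 of 4. Not named: 4 − 2 = 2.

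**Step 2. The wider retention discussion in 6.3.1.** The same part of 6.3.1 also mentions dysphagia (item 3), gastroparesis (item 5) and Crohn's disease (item 6). Adding these three gives 4 + 3 = 7 conditions, of which 2 + 3 = 5 are covered. The same two are missing. This second count is looser, because dysphagia and swallowing disorder share one item and gastroparesis is mentioned there chiefly for capsule retrieval. It does show that everything else in the discussion was carried over, which points to an oversight and not a choice.

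**Step 3. A catch-all in 10.2.** The other eight items are shock, active hematemesis, pregnancy or breastfeeding, altered mental status, expected MRI, no reliable contact information, pacemaker or ICD, and BMI of 38 or more. None is a general clause on retention risk or investigator judgement.

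**Step 4. The inclusion criteria.** None of the five items in Section 10.1 rules these people out. The closest is item 4, "Able to undergo standard outpatient endoscopy", which concerns fitness for the EGD and not whether a capsule will pass. Item 5 ends with an open category of other indications.

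**Step 5. Who falls through.** Items 3 to 7 remove many people with a stricture or fistula. A candidate remains eligible if all of these hold:

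- the stricture or fistula is not due to Crohn's disease;
- there is no dysphagia or swallowing disorder;
- no obstruction is suspected;
- there is no gastroparesis;
- there has been no anatomy-changing surgery.

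Such a person can plausibly be referred, since Section 9.4 recruits patients with abnormal imaging that suggests organic disease.

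**Step 6. Size.** The document gives no prevalence for this group. It puts capsule retention in general below 1% and adds that the figure may be higher in Crohn's disease or other conditions. It gives no rate for strictures or fistulas, so neither the number of candidates nor the added risk can be calculated.

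**The case against.** The strongest reply is that this is an omission and not a conflict. Section 10.2 nowhere says these people are eligible, and an investigator who follows the whole protocol would not enrol them. Section 6.3.1 also holds another enrolment limit that 10.2 does not repeat: "Patients for whom study enrollment may interfere with standard clinical care will not be enrolled". This stands as a description, and the list is best read as incomplete. It does not remove the problem, because Sections 9.4 and 17.4 present the criteria as a full list.

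Second, Section 6.1 calls intestinal obstruction the only absolute contraindication, and obstruction is in 10.2. That is a statement about capsule endoscopy in general. Section 6.3.1 sets a stricter rule for this study, and that rule is the one not carried out.

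Third, there are safeguards. The PI takes part in the final interview, and the capsule is "administered the MCC under the supervision of a physician". The PI may withdraw a patient for serious medical conflicts (Section 10.4.1). Calls follow on days 7 and 30, and an X-ray or capsule locator can confirm passage. These lower the risk, but none states the missing criterion, and the calls and the X-ray or locator act only after the capsule has been swallowed.

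Fourth, the eligibility screening form (Magnet 2 in Appendix B) is not shown and may already ask about strictures and fistulas. If it does, the practical harm shrinks and what remains is a mismatch between form and protocol. That cannot be settled from the document.

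**Conclusion.** The point holds. Section 10.2 is incomplete as written: it leaves out two of the four conditions that Section 6.3.1 names as making a person unsuitable, and no other item in Section 10 supplies them.

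The wording gap is certain. Its practical effect is probably small, because overlapping exclusions and physician involvement narrow the group. How small depends on an unseen form and on a prevalence that the document does not give. No estimate, stated figure or analysis changes, and the sample size of 72 is unaffected. The omission should still be corrected, because it concerns a stated safety limit tied to a potential major adverse event.

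**What to change.** Add one item to Section 10.2: *known or suspected gastrointestinal stricture or fistula*. Check that the Magnet 2 screening form asks about both conditions, and add the question if it does not. While the list is open, item 4 could be widened from suspected to known or suspected obstruction, to match Section 6.3.1.

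The cost is one added line, a check of one form, and IRB approval of the amendment, which Section 17.2 requires before the change takes effect. Recruitment should hardly be affected, since few candidates are likely to meet the new item.

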will be pre-determined, and each area will have a predetermined number of images obtained as suggested by Gastroenterology Society guidelines.

5. Patient data collected will include the following elements: chief complaint of patient, history of present illness, past medical history, current medications (only PPIs and pain medication)..
6. At completion of MCC, video will be archived and patient satisfaction will be assessed. Capsule endoscopy will NOT be used for clinical decisions.
7. Patients will be instructed to return to the physician sooner, if concerning signs develop. A 7 and 30-day follow-up call and chart review is only performed if person is lost to follow-up will be conducted to check for symptom resolution and adverse events.
8. Esophagogastroduodenoscopy (EGD) will be performed as soon as possible in an appropriate endoscopy facility by an experienced endoscopist.
9. Endoscopic images will be stored in secure serve for later comparison with MCC images.

Summary of Research Strategy

- ❖ PRE-SCREEN (DAY -7 to DAY -1)
 - Upper Abdominal Pain or Related Symptoms (Indications for an EGD)
 - Performed in ED, UC, PCP offices or GI clinic
- ❖ SCREEN (DAY -7 -> DAY 0)
 - More thorough screening questions and scheduling by RC (<24 hours)
 - Performed by Telephone
- ❖ ENROLL (DAY 0)
 - Signed Informed Consent procedure, more detailed questions and MCC Procedure performed
 - Occurs at the GWU Medical Faculty Associates Building on [name].
 - NaviCam MCC performed by trained Clinician.
 - Reviewed by a Gastroenterologist.
 - Scheduled for an EGD will ideally be performed within 5 days of the MCC procedure, but will allow MCC procedure to be performed up to 14 days either before or after an EGD (paid by insurance as standard of care).
- ❖ FOLLOW-UP (DAY 1-30)

- Day 7 and Day 30: Telephone Call plus CRISP Chart Review, only if lost to follow-up.

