13.2. Sample Size Considerations

The sample size for this Proof of Concept study was not chosen for statistical consideration, as there are no formal statistical inferences planned. The size of the study is judged adequate for the preliminary evaluation objectives. All 72 participants will receive the MCC and will be referred to follow-up EGD. The base-line prevalence of lesions and the estimated loss to follow-up will provide information for formal sample size calculation for follow-up study.

We did not use a statistical justification but a practical justification to choose 72 participants. All 72 will get the MCC unless they are unable to tolerate the capsule. The issue of drop-out is relevant only to Aim 3 which pilots the concept of non-inferiority compared to subsequent EGD. We did not power this study to prove non-inferiority --- this study will allow us to estimate baseline lesion prevalence and the likely drop-out rate. Moving forward, we will be able to calculate an accurate sample size for a future larger definitive non-inferiority study.

For patients in whom visualization is limited by incomplete gastric emptying, we will record fasting time but exclude patient from assessment of MCC accuracy.

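### Section 6.3.1 discounts the risk of a capsule held in the upper tract because every patient has an EGD, but section 9.4 lets the EGD come first, when retrieval could need a second EGD caused by the study

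*Protocol*

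**What the plan says.** Section 6.3.1 (Potential Risks) accepts that the capsule could lodge in the stomach or small intestine. For a capsule that stays in the upper tract because of gastroparesis, it says that in general "an EGD will be sufficient to retrieve the capsule". It then gives its reason for setting this risk aside: "all study patients will receive an EGD as part of their standard work-up for the disease, this does not pose a significant increased risk". The same section puts capsule retention below 1% and adds: "The rate of surgical/endoscopic removal was noted to be 0.75" per cent.

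Section 9.4 (Study procedure) sets the order of the two tests. The coordinator is to "schedule both MCC and EGD (if EGD is not already scheduled"), and no order is fixed there. The Summary of Research Strategy in the same section aims for an EGD within 5 days of the capsule, but "will allow MCC procedure to be performed up to 14 days either before or after an EGD".

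Section 10.2 excludes gastroparesis, Crohn's disease, dysphagia, suspected obstruction and surgically altered anatomy.

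**The concern.** The argument in 6.3.1 treats the clinically indicated EGD as a retrieval procedure that the patient would undergo anyway. That needs the EGD to be still ahead when the capsule is swallowed. The two-way window in 9.4 permits the opposite order, and 6.3.1 does not mention participants scoped first.

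For them, endoscopic retrieval would be a further procedure, needed only because they joined the study. The protocol does not treat an EGD as trivial: section 6.1 lists cost, "the need for an endoscopy specialist and the need for anesthesia" among the limits on access to it. Section 6.3.1 is the protocol's statement of physical risk, so an ethics board or the DSMB would rely on it. No endpoint or analysis depends on this point.

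**Working it through.** The protocol gives no calculated figure on this point, so there is nothing to reproduce. The check is mainly one of sequence.

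**Step 1: the two permitted orders**

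| Order under 9.4 | Work-up EGD still to come when the capsule is swallowed? | Consequence if the capsule is held up and needs an EGD |
|---|---|---|
| Capsule first, EGD afterwards | Yes | The planned EGD can serve for retrieval; the reason in 6.3.1 applies |
| EGD first, capsule up to 14 days later | No | Retrieval is an additional EGD, caused by the study; the reason in 6.3.1 does not apply |

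The second row is expressly allowed, and no other section limits the statement in 6.3.1 to the first row.

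**Step 2: size per EGD-first participant**

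- Input: removal rate r = 0.75% = 0.0075 (6.3.1).
- 1 / r = 1 / 0.0075 = 133, so about 1 in 133.

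I treat this as an upper bound, for three reasons:

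- It counts surgical and endoscopic removal together and is not limited to capsules held in the stomach.
- It is cited to a 2002 source, whereas 6.3.1 dates this device's Chinese approval to 2012. It therefore describes other capsules.
- It is not restricted to patients who meet this trial's exclusions.

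The rate that would answer the question directly, gastric hold-up needing an EGD in a population screened as in 10.2, is not in the protocol.

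**Step 3: size for the trial**

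Let s be the share of the 72 participants who have the EGD first. The expected number of additional EGDs is at most 72 × s × 0.0075. The protocol does not give s. At s = 0 the result is 0; at s = 1 it is 72 × 0.0075 = 0.54. These are the arithmetic limits only. Nothing in the protocol supports a particular value between them, so I give no probability for the trial as a whole.

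**The case against.** The strongest reply is that the reason in 6.3.1 is correct for the sequence the protocol mainly has in mind. In the steps of 9.4 the EGD is listed after the capsule, and 13.2 speaks of a subsequent EGD: "All 72 participants will receive the MCC and will be referred to follow-up EGD". Section 8.3.6 likewise pictures an EGD a few days later. The sentence in 6.3.1 is also narrow: it concerns hold-up from gastroparesis, which is an exclusion criterion, so only residual or unrecognised cases remain.

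All of this stands, and it makes the point small. It does not remove it. The window in 9.4 is the operative scheduling rule and allows both orders. By discussing gastroparesis despite the exclusion, the protocol itself recognises a residual case.

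Three stronger readings are tempting, and the protocol does not support them.

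- **That the trial's low-risk judgement is wrong.** A reader might infer this from the failed reason. But retention below 1% and the exclusions in 10.2 support the judgement without it.
- **That the need for removal is concealed.** Section 6.3.1 states that the capsule may lodge in the stomach, gives the removal rate and names EGD as the means of retrieval. Only the EGD-first group is not singled out. The manufacturer has also agreed to cover research injuries, on terms still under negotiation, though that addresses cost and not the procedure. The consent pages are not available, so what participants are told cannot be judged.
- **That participants who never attend their EGD face the same extra procedure.** The protocol summary speaks of enrolling patients "with a goal of following all patients with a traditional endoscopy to confirm findings", and 13.2 expects some drop-out, so not everyone need be scoped. But non-attenders have an indication for EGD that has not yet been met. A retrieval EGD for them would be unplanned, not additional.

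**Conclusion.** The point holds in a limited form. The reason in 6.3.1 does not cover participants who have the capsule after their EGD. Those participants could need a second EGD if the capsule is held in the upper tract.

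The chance is below about 0.75% per EGD-first participant. This assumes that the quoted removal rate, taken from other capsules, is an upper bound for gastric retrieval here. If in practice every capsule is followed by an attended EGD, the effect is nil. The correction concerns the safety rationale and the booking order, and it is minor.

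**What to change.** 1. In 6.3.1, limit the sentence to participants whose EGD follows the capsule. State that a participant scoped first could need an additional EGD if the capsule is held in the upper tract. Rest the low-risk judgement on the reported retention rate below 1% and the exclusions in 10.2.
2. In 9.4, have the coordinator book the capsule before the EGD wherever the EGD has not yet been done and clinical care is not delayed. Keep the 14-day allowance in both directions for everyone else.

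The existing X-ray or locator check for patients unsure of passage can stay as it is; the inconsistency does not call for a broader imaging rule.

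The cost is a short rewording in 6.3.1 and one scheduling line in 9.4. The coordinator already arranges both tests, so the only practical downside is slightly tighter booking of the capsule when an EGD date is already near.
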